Buprenorphine Adherence and Opiate Abstinence and Buprenorphine Adherence Only participants will receive incentives for daily buprenorphine use. Buprenorphine Adherence and Opiate Abstinence participants also will receive incentives for providing opiate-negative saliva samples. Daily buprenorphine use and opiate abstinence will both be remotely verified using smartphone-enabled video directly observed therapy (Video DOT) provided by emocha Mobile Health, Inc. The incentives will be integrated into the Video DOT platform and delivered remotely to reloadable credit cards. Participants will be assessed every month during a 3-month intervention period and every 3 months during a 9-month follow-up period. The primary outcome measures will be a) opiate abstinence and b) buprenorphine adherence during the 3-month intervention as assessed by urinalysis results every month during the intervention. If the proposed intervention is effective, it could improve patients' access to and success in office-based buprenorphine treatment.

2. Objectives (include all primary and secondary objectives)

Primary Aims

- Determine effectiveness of Contingency Management compared to Usual Care in promoting buprenorphine adherence and opiate abstinence as assessed by urine drug screens during the intervention.

Secondary Aims

- Determine effectiveness of Contingency Management compared to Usual Care in: a) reducing buprenorphine diversion, b) promoting retention in buprenorphine treatment, c) reducing opioid overdose and risk of overdose, d) improving psychosocial functioning and quality of life, e) promoting patient treatment satisfaction, and f) maintaining any effects after the intervention period ends.

3. Background (briefly describe pre-clinical and clinical data, current experience with procedures, drug or device, and any other relevant information to justify the research)

Opioid use has increased to epidemic levels in the United States and is a major cause of morbidity and mortality nationwide.¹⁻⁴ In 2016 alone, more than 42,000 people died from an overdose involving

Date: April 12, 2023

Principal Investigator: [name]

Application Number: IRB00220692

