To increase the chance that we engage participants, during an initial 7-day period, participants will be offered access to the study smartphone app and incentives. We have used similar induction procedures in our prior studies to successfully engage participants. Participants will have the smartphone app installed on their smartphones and will be taught how to use the app. Participants will then be asked to use the application to record a video of themselves for 7 days. Each video will be uploaded into a web portal, which can be securely accessed by our research staff, and will be reviewed by our research staff. Participants will be able to earn \$10 per day over the 7-day period for submitting a video of themselves each day. Participants who use the smartphone application to record and submit videos on 6 or more days during the 7-day induction period will be randomly assigned to a study group (as described in detail below).

Experimental Design

Participants (N=375) will be randomly assigned to one of two Contingency Management groups—a Buprenorphine Adherence and Opiate Abstinence group and a Buprenorphine Adherence Only group—or a Usual Care (Control) group. A computerized urn randomization procedure will be used to randomize participants and to balance groups on three characteristics that may influence outcome: (1) opioid use severity (used illicit opioids ≥ 15 days out of the past 30 days, Y/N), (2) cocaine use (cocaine-positive urine, Y/N), and (3) age (greater than rolling median, Y/N). Participants will be stratified by opioid use, cocaine use, and age because each has been associated with buprenorphine treatment outcomes.⁶⁵⁻⁶⁷ Participants will be assessed every month during the 3-month intervention and every 3 months during a 9-month follow-up period. We will teach participants the details of their study group with instructions and quizzes.

General Contingency Management Procedures

Both Contingency Management groups (Buprenorphine Adherence and Opiate Abstinence and Buprenorphine Adherence Only participants) will receive incentives for daily buprenorphine use. Buprenorphine Adherence and Opiate Abstinence participants also will receive incentives for providing opiate-negative saliva samples. Both of the Contingency Management interventions will have the following

Date: April 12, 2023

Principal Investigator: [name]

Application Number: IRB00220692

features:

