Assessments will be conducted at intake, every month during the 3-month intervention period, and at 6, 9, and 12 months after randomization. Participants will be paid \$50 for completing each of the intake and monthly assessments, and \$100 for completing the follow-up assessments. These assessments will be collected using REDCap. Whenever possible, assessments will be conducted remotely via phone or web-conferencing.

Intake Only Assessment Instruments

DSM-5 Checklist for Opioid Use Disorder. The DSM-5 checklist for opioid use disorder is a structured assessment that will be used to determine if participants have opioid use disorder.

Non-Study Medical and Other Services – NSMOS-BL. This assessment will be used to collect information on medical services participants may have received in the 3 months prior to study intake.

Intake and Major Assessment Instruments

Urine and saliva toxicology testing. Urine and saliva samples will be collected and tested for opioids and other drugs. Toxicology testing may be conducted by sending a testing kit to participants through the mail. Participants would then be asked to complete the toxicology tests (urine and saliva) and provide a video showing the results of the tests using the study smartphone app.

Time-line follow-back (TLFB). Participants will be asked whether or not they are in treatment for their opioid use disorder, including treatment other than buprenorphine (e.g., methadone maintenance). For participants who report being in buprenorphine treatment, the TLFB procedure will be used to elicit participants' self-reported taking of their buprenorphine dose each day. Pharmacy and/or clinic records (with participant permission) may be used to confirm self-reported data.

Opioid Overdose Risk Assessment. An opioid overdose risk assessment will be used to assess the rate at which participants report engaging in behaviors that may put them at risk for an opioid overdose.

The Addiction Severity Index – Lite (ASI-Lite). The ASI-Lite is a structured interview designed to assess problem severity in areas commonly affected by drug and alcohol use (medical, legal, employment, family/social, and psychiatric) with good reliability and validity.

Smartphone Form. This questionnaire will document participants' access to and willingness to use a smartphone during the study.

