Treatment Acceptability Questionnaire. To assess the acceptability of our intervention, we will administer a Treatment Acceptability Questionnaire to participants who are exposed to our smartphone incentive intervention at the end of the 3-month intervention period.

Client Satisfaction Questionnaire (CSQ-8). To assess patient treatment satisfaction, we will use the CSQ-8, a brief (8-item) validated instrument that has been used widely across health services.

Short Form (SF-36). We will assess self-reported quality of life using the 36-item short-form survey instrument.

Non-Study Medical and Other Services – NSMOS-FU. This assessment will be used to collect

Date: April 12, 2023

Principal Investigator: [name]

Application Number: IRB00220692

information on medical services participants may have received during the intervention.

Northern Michigan University

This protocol is a multi-site study (See Section 1, Question 9). The Center for Learning and Health, Johns Hopkins University School of Medicine will serve as the lead/coordinating center for this multi-site study (See Section 1, Question 9) and JHM IRB will serve as the single IRB of record for this protocol (See Section 1, Question 10).

Northern Michigan University will serve as the second site in this study. Northern Michigan University will assist in overseeing the entire project, providing PCORI with needed information and documents, managing the Data Safety Monitoring Committee, managing the Study Advisory Committee, preparing the data for analyses, preparing reports required for PCORI, and preparing and submitting manuscripts for publication and presentation. [name] is a co-investigator on this project and will serve as the PI for Northern Michigan University. [name] is an Assistant Professor at Northern Michigan University. Under [name] supervision, research assistants will work with research staff at Johns Hopkins University School of Medicine to prepare the study data for analyses, and summarize and graph data for reports, publication, and presentation.

b. Study duration and number of study visits required of research participants.

Study participation will include a 3-month intervention evaluation period and a 9-month follow-up period for a total study duration of 12 months. Outcome assessments will be conducted at intake, every month during the 3-month intervention period, and at 6, 9, and 12 months after randomization.

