Opiate Abstinence. We will assess the percentage of participants with opiate-negative urine samples (excluding buprenorphine and methadone if self-report confirms that the participant is enrolled in buprenorphine or methadone treatment) at the monthly assessments during the 3-month intervention evaluation period (Yes/No at each assessment).

b. Secondary outcome variables.

Buprenorphine Diversion. We will assess the number of days participants report diverting their daily buprenorphine dose (selling or giving their buprenorphine dose to someone else) during the 28 days prior to each of the monthly assessments during the 3-month intervention evaluation period (based on TLFB).

Retention in Buprenorphine Treatment. We will assess the last day that participants reported taking buprenorphine during the 3-month intervention evaluation period (based on TLFB).

Overdose risk. We will assess the rates at which participants report engaging in overdose risk behaviors at the monthly assessments during the 3-month intervention evaluation period (based on total scores from the opioid overdose risk assessment).

Psychosocial Functioning. We will assess patient-reported psychosocial functioning during the 3-month intervention evaluation period (based on the ASI-Lite).

Quality of Life. We will assess patient-reported quality of life during the 3-month intervention evaluation period (based on scores from the SF-36).

Patient Treatment Satisfaction. We will assess patient-reported treatment satisfaction during the 3-month intervention evaluation period (based on scores on the CSQ-8).

Post-Intervention Effects. We will assess the outcomes described above every 3 months during a 9-

Date: April 12, 2023

Principal Investigator: [name]

Application Number: IRB00220692

month follow-up after the intervention ends.

c. Statistical plan including sample size justification and interim data analysis.

Statistical Analyses

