We will analyze measures assessed repeatedly over time with a longitudinal logistic regression model. Within-person correlated outcomes will be handled using generalized estimating equations (GEE; Zeger, Liang, & Albert, 1988). Measures assessed once will be analyzed using logistic regression. The magnitude of effects will be expressed using odds ratios with 95% confidence intervals. Retention in buprenorphine treatment during the intervention period will be analyzed with a Cox proportional hazards model. We will adjust the intent-to-treat analyses for covariates used for stratification (Pocock, Assmann, Enos, & Kasten, 2002).

Primary outcome analyses. We will fit a longitudinal logistic regression model $\text{logit}(Y_{ij}) = \beta_0 + \beta_1 tx_1 + \beta_2 tx_2 + \beta_3 x_{2-4} + \varepsilon_{ij}$, where Y_{ij} is evidence of buprenorphine adherence or opiate abstinence for the i th person at the j th timepoint (3 visits over 12 weeks), β_1 is the covariate of interest representing the expected increase in log odds of evidence of buprenorphine adherence or opiate abstinence as a function of assignment to the treatment group, and β_{2-4} are the coefficients for the 3 randomization covariates. We also will fit models with time and time by treatment interactions to look at change over time in buprenorphine adherence and opiate abstinence in each study group.

Secondary outcome analyses. We will fit longitudinal logistic regression models for the secondary measures. We will assess effects during the 3 months by fitting analogous models as described above for each outcome, including fitting models to look at change over time in each study group. Retention in buprenorphine treatment will be analyzed using a Cox proportional hazards model.

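### The secondary-score models adjust only for the three randomization covariates and leave out each score's own intake value, giving up power on secondary aims c and d (and e, if the CSQ-8 is given at intake)

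*Combined protocol and SAP*

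**What the plan says.** Section 2 lists among the secondary aims "c) reducing opioid overdose and risk of overdose, d) improving psychosocial functioning and quality of life, e) promoting patient treatment satisfaction". Section 7.b ties these to the opioid overdose risk assessment, ASI-Lite, SF-36 and CSQ-8. The overdose-risk outcome, for example, is "based on total scores from the opioid overdose risk assessment".

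Section 7.c sets the adjustment for all the analyses: "We will adjust the intent-to-treat analyses for covariates used for stratification". It writes the primary model with two treatment terms and three randomization covariates, over three visits in 12 weeks. For the secondary outcomes it then says "We will assess effects during the 3 months by fitting analogous models as described above for each outcome". It names logistic regression with GEE for them and reports effects as odds ratios.

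Section 4.a, Experimental Design, defines the covariates: "A computerized urn randomization procedure will be used to randomize participants and to balance groups on three characteristics that may influence outcome". They are illicit opioid use on at least 15 of the past 30 days, a cocaine-positive urine, and age above a rolling median. None is a secondary score.

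On timing, section 4.a states: "Assessments will be conducted at intake, every month during the 3-month intervention period, and at 6, 9, and 12 months after randomization". All four instruments stand under the heading "Intake and Major Assessment Instruments".

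**The concern.** A participant's intake score on quality of life, functioning or risk behaviour can be expected to predict the later score. The plan collects that value before randomization and then does not use it. The models for time and time by treatment do not bring it in, because the outcome timepoints are the three post-randomization visits and intake is not named as one of them. The urn does not balance on these scores either.

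At stake are power for the secondary scores and protection against an unlucky intake difference between groups. There is also a reason to settle this in advance: participants are not blinded (section 4.c), and a baseline covariate added once results are known would be a post hoc choice.

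**Working it through.** **The plan's own figure.** Section 7.c needs 106 evaluable per group with 15% missing: 106 / 0.85 = 124.7, so 125 per group, and 3 × 125 = 375. This reproduces. The 106 itself (68% vs 83%, 80% power) depends on a within-person correlation that is not stated. One visit needs about 128 per group, and 127.9 × (1 + 2 × 0.743)/3 = 106, so the implied correlation is about 0.74. Other variance formulas put it between 0.70 and 0.77. No power figure is given for any secondary score.

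**Assumptions for the secondary scores.** 106 per group, two groups compared, two-sided 5%, the mean of the three monthly visits as the contrast, score SD of 1. Let r be the correlation between intake and each visit, and ICC the correlation between visits. None of these correlations is in the documents. Two cases are shown: ICC equal to r, and ICC = 0.7 (in line with what the 106 implies for the primary outcome).

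**Linear model of the score.** Variance of the three-visit mean: V = (1 + 2 × ICC)/3. Fraction removed by the intake value: R² = r²/V. For an effect with 80% power unadjusted, adjusted power = Φ(2.80/√(1 − R²) − 1.96).

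| r | R², ICC = r | Power | R², ICC = 0.7 | Power |
|---|---|---|---|---|
| 0.2 | 0.04/0.467 = 9% | 83% | 0.04/0.8 = 5% | 82% |
| 0.3 | 0.09/0.533 = 17% | 87% | 0.09/0.8 = 11% | 84% |
| 0.5 | 0.25/0.667 = 38% | 94% | 0.25/0.8 = 31% | 92% |
| 0.7 | 0.49/0.8 = 61% | 99% | 0.49/0.8 = 61% | 99% |

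Smallest difference detectable with 80% power at r = 0.5: 2.80 × √((2/106) × 0.667) = 0.31 SD unadjusted and 2.80 × √((2/106) × 0.417) = 0.25 SD adjusted when ICC = r. With ICC = 0.7 it falls from 0.34 to 0.29 SD (0.344 to 0.285).

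**Logistic GEE, the family the plan names.** The plan gives no cut-point, so a dichotomized score was assumed. Two simulations were run, each with a stratification covariate in both models. The first used a true shift of 0.3 SD, 106 per group, ICC = r and 500 runs per setting.

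| r | Power without → with intake, first | Second | Gain in points |
|---|---|---|---|
| 0.3 | 74% → 79% | 74% → 76% | 2–5 |
| 0.5 | 67% → 81% | 69% → 80% | 11–14 |
| 0.7 | 59% → 86% | 68% → 84% | 16–27 |

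At r = 0.7 in the first simulation, the standard error of the log odds ratio rose from 0.229 to 0.244, while the estimate rose from 0.50 to 0.75. In the second the standard error rose from 0.232 to 0.243. The gain is in power. It comes because the odds ratio conditional on intake is further from 1 (non-collapsibility).

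**Chance imbalance.** With 125 per group, the intake difference between two groups has standard error √(2/125) = 0.126 SD, so about 5% of comparisons exceed 1.96 × 0.126 = 0.25 SD. At r = 0.5 about half of that, 0.12 SD, carries into follow-up, against a detectable difference of about 0.31 SD.

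**The case against.** The case for leaving the plan alone is reasonable. Adjusting for the stratification factors is a valid pre-specified analysis, the trial is powered on the primary outcomes only, and nothing in the documents shows that intake values predict follow-up strongly. Opioid-use severity, already a covariate, may recover part of the overdose-risk gain. All of this stands, and it is why the point is an improvement and not an error.

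Three stronger readings are tempting, and the documents do not support them.

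- A reader might infer that the omission biases the secondary comparisons. It does not. Randomization keeps them valid, and the error rate of the test already allows for chance imbalance. What is lost is efficiency.
- A reader might infer that the planned confidence intervals are too wide. That holds for a linear model of the score. In the logistic model that 7.c names, adjustment did not narrow the interval on the log odds scale, and it changes the target to an odds ratio conditional on intake.
- A reader might infer that all four scores certainly have an intake value. For the CSQ-8 ("To assess patient treatment satisfaction, we will use the CSQ-8") this rests on the heading alone. The same heading covers the Treatment Acceptability Questionnaire, limited to the end of month 3, and the follow-up services form, which covers the intervention period. Aim e is therefore conditional.

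It is also fair that logistic models for scores need a cut-point that the plan does not give, and that the ASI-Lite covers several problem areas without a named score. Those matters need settling too. They do not remove the point, because power rises under both model forms.

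**Conclusion.** The point holds as a free improvement. The secondary models use only the three randomization covariates although the overdose risk, ASI-Lite and SF-36 scores are available before randomization. The comparison is valid but gives up power and protection against chance imbalance on aims c and d, and on e if the CSQ-8 is given at intake.

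The size rests on assumed correlations. It is modest at 0.3, substantial at 0.5 and large at 0.7. At 0.2 it is close to negligible. The lower end of each linear range applies when visits correlate more strongly with one another (0.7) than with intake. The logistic figures assume a dichotomized score, and the spread between the two simulations shows how far they depend on the settings.

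**What to change.** In section 7.c, Secondary outcome analyses, add:

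> Each model for a secondary score that is collected at intake (opioid overdose risk total score, each analysed ASI-Lite score, each analysed SF-36 score, and the CSQ-8 where collected at intake) will also include the participant's intake value of that same score as a covariate, in addition to the three randomization covariates, both during the intervention and at months 6, 9 and 12. Any missing intake value will be replaced by the overall intake mean and not imputed as adverse.

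Keep the model with randomization covariates only as a sensitivity analysis. If the logistic form is kept, state that the adjusted odds ratio is conditional on the intake score.

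The cost is two sentences and one degree of freedom per model. No new data, visits or staff are needed. The team should also confirm whether the CSQ-8 is given at intake.

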Missing data. We expect to collect $\geq 85\%$ of the study assessments. Our primary approach to handle missing data will be to impute missing values as the adverse outcome (e.g., buprenorphine-negative urine sample). Model parameter estimates from this approach will be compared to a method without imputation. If these methods yield differing results, conclusions will need to be tentative, but results from both approaches will be reported in publications. To investigate sensitivity to missing values, participants with and without missing values will be compared by covariates and group assignment. If rates are higher than expected, we may use mixed effects models rather than GEE estimation, as the former has less strict assumptions regarding missing data (missing at random, rather than missing completely at random).

Power Analyses

We used Liu and Liang⁸⁴ to determine the number of participants required to detect a difference of 15% between groups using the three monthly assessments during the 3-month intervention period with 80% power and adjusting for missing data (15% missing). Based on these analyses, we will randomize a total of 375 participants (125 per group).

Buprenorphine adherence. We expect a fairly large difference in buprenorphine adherence between the two Contingency Management groups and the Usual Care group. Specifically, we expect that each Contingency Management group will provide urine samples positive for buprenorphine on 85% of the assessments, whereas we expect that the Usual Care group will provide urine samples positive for buprenorphine on 45% of the assessments. Thus, we expect to obtain a 40% difference in buprenorphine adherence between each of the Contingency Management groups and the Usual Care group.

Opiate abstinence. We expect large differences in opiate abstinence between each of the two Contingency Management groups and the Usual Care group, but a relatively small difference in opiate abstinence between the two Contingency Management groups. The Power Analysis was designed to allow

Date: April 12, 2023

Principal Investigator: [name]

Application Number: IRB00220692

us to detect the smallest difference in opiate abstinence between groups: the difference between the Buprenorphine Adherence Only (expected 68% opiate negative) and the Buprenorphine Adherence and Opiate Abstinence (expected 83% opiate negative) groups; to detect this difference, we would need 106 participants.

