Total sample size. Based on the analyses described above, we would need 106 participants per group to detect effects between the pairs of groups for the planned comparisons. After adjusting for the anticipated rates of missing data (15% missing), we need to randomize 125 participants to each of the three groups to ensure that we have sufficient sample sizes (125 participants x 0.85 collected assessments = 106 participants per group). Thus, we will randomize a total of 375 participants.

d. Early stopping rules.

The study investigators and a Data Monitoring Committee (DMC) will provide data and safety monitoring of the proposed trial. To monitor adverse events, all staff members who have regular contact with study participants are instructed on the need to report to an investigator any indication that an adverse event has occurred. When the staff members and investigators learn of an adverse event, they will investigate until they have determined as many of the relevant details of the adverse event as possible. To provide consistent monitoring of adverse events across groups, participants will be asked about all categories of adverse events at each routine assessment visit conducted throughout the study. At least one investigator will review each adverse event as it occurs. The DMC will review a summary of adverse events annually. This frequency of review will be increased if the adverse events occur at a higher rate than anticipated. The protocol can be stopped based on recommendations of the investigators or DMC who are reviewing the adverse events in the study. We will ask the investigators and DMC to recommend that the trial be stopped if a review of the adverse events suggests to any of the investigators or DMC members that the number of related adverse events is unacceptably high. The investigators or DMC will be allowed to request statistical analyses to compare the groups on the rates of different adverse events or to have the adverse event data summarized in other ways that they deem appropriate.

8. Risks

a. Medical risks, listing all procedures, their major and minor risks and expected frequency.

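### The stated 80% power treats the 15% missing results as lost sample, but the primary analysis scores them as adverse; on the plan's own values, power for 68% vs 83% falls below 80%

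*Combined protocol and SAP*

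**What the plan says.** All references are to section 7c of the combined protocol and SAP unless noted.

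- **Missing data.** The primary rule is worst-case scoring: "Our primary approach to handle missing data will be to impute missing values as the adverse outcome (e.g., buprenorphine-negative urine sample"). An analysis without imputation is run for comparison. The plan expects at least 85% of assessments to be collected.
- **Power Analyses.** The trial is sized to detect a 15-point difference over three monthly assessments "with 80% power and adjusting for missing data (15% missing").
- **Opiate abstinence.** The contrast that sets the sample size is "the difference between the Buprenorphine Adherence Only (expected 68% opiate negative") and "the Buprenorphine Adherence and Opiate Abstinence (expected 83% opiate negative) groups". The result is 106 participants per group.
- **Total sample size.** The allowance for missing data is "125 participants x 0.85 collected assessments = 106 participants per group", hence 375 randomized in total.
- **Not stated.** Neither alpha nor the within-person correlation is given for the power calculation. The nearest indication of alpha is under Statistical Analyses: "The magnitude of effects will be expressed using odds ratios with 95% confidence intervals".
- **Section 2, Primary Aims.** The aim is worded against Usual Care: "Determine effectiveness of Contingency Management compared to Usual Care in promoting buprenorphine adherence and opiate abstinence".

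**The concern.** Dividing by 0.85 is right when missing results drop out of the analysis: fewer observations remain and the two rates stay at 68% and 83%. Under the primary rule nothing drops out. All 125 participants per group contribute three results each, and the uncollected ones are counted as opiate-positive. That lowers both rates and narrows the gap between them. If misses cluster within people, it also raises the within-person correlation. The inflation to 125 replaces lost observations but does not correct for a smaller effect.

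The 80% is the only power figure in the plan, and the plan says this contrast set the sample size. A null result between the two Contingency Management groups would be read against a power that the primary analysis does not have.

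**Working it through.** **Inputs from section 7c.** Rates 68% and 83%; three visits; 106 per group, inflated to 125; 15% missing; 80% power.

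**Assumptions, because the plan is silent.** Two-sided alpha 5%, in line with the 95% confidence intervals. Exchangeable within-person correlation ρ, back-solved so that 106 per group gives 80%. The same 15% missing in both groups. The 68% and 83% are rates among collected samples.

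**1. The plan's own figure.** On the logit scale:

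n = (1.960 + 0.842)² × [1/(0.68 × 0.32) + 1/(0.83 × 0.17)] / (ln 2.298)² × (1 + 2ρ)/3

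= 7.849 × (4.596 + 7.087) / 0.692 × (1 + 2ρ)/3 = 132.5 × (1 + 2ρ)/3

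This equals 106 at ρ = 0.70. The risk-difference version is 125.1 × (1 + 2ρ)/3, which equals 106 at ρ = 0.77. So 106 can be matched but not confirmed, because the plan gives no ρ. The inflation reproduces: 106/0.85 = 124.7, rounded up to 125.

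**2. Rates under the primary rule.** 0.68 × 0.85 = 57.8% and 0.83 × 0.85 = 70.55%. The difference is 12.75 points instead of 15, and the odds ratio is 1.75 instead of 2.30.

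**3. Variance under the primary rule.** The scored result is Z = Y × R, where Y is opiate-negative and R is collected. Let c be the collection rate and k the within-person correlation of collection. Then

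Cov(Z at two visits) = [p² + ρp(1 − p)] × [c² + kc(1 − c)] − (pc)²

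and the variance of a person's three-visit mean is [pc(1 − pc) + 2 Cov]/3.

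On the logit scale with ρ = 0.70, c = 0.85 and n = 125, the log odds ratio is 0.559. Its standard error is 0.206 for k = 0, 0.228 for k = 0.5 and 0.249 for k = 1. Power is Φ(0.559/SE − 1.96).

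**4. Power at 125 per group.** Each cell gives logit, then risk difference:

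| Missing in each group | Independent misses (k = 0) | Moderately clustered (k = 0.5) | Same people miss all visits (k = 1) |
|---|---|---|---|
| 15% | 77.4%, 76.3% | 68.7%, 68.0% | 61.3%, 61.0% |
| 10% | 80.9%, 79.8% | 74.8%, 74.2% | 69.3%, 69.1% |
| 5% | 83.8%, 83.1% | 80.7%, 80.3% | 77.7%, 77.6% |
| Largest missing rate that keeps 80% | 11.3%, 9.8% | 5.6%, 5.3% | 3.6%, 3.6% |

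A simulation of 20,000 trials (logit Wald test, person-level robust variance, ρ = 0.70) gave 77.8%, 69.0% and 61.0% at 15% missing.

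**5. Same n without imputation.** At 15% missing, power is 83.6% (k = 0), 81.8% (k = 0.5) and 80.1% (k = 1) on the logit scale. This is the analysis that the stated 80% fits.

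**6. Unequal collection (illustrative; the plan gives one rate only).** With 84% collected in Adherence Only and 86% in the combined group, power is 71–86%. With the reverse, it is 50–67%.

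**7. Other alphas.** Recalibrated so that 106 still gives 80%, power at 15% missing is 55–75% at two-sided 0.025 and 52–73% at 0.0167.

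**8. Adherence against Usual Care.** 85% vs 45% becomes 72.25% vs 38.25%. Power is above 99% even from a single visit. The abstinence contrast with Usual Care cannot be computed, because the plan gives no expected Usual Care abstinence rate.

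**The case against.** - **The correlation and alpha are reconstructed.** True, so the magnitudes are conditional. With ρ of 0.6 or less and independent misses, 125 would still give 80% after imputation. But then 106 would not be the n for 80%, which is what the plan says it is.
- **15% is the limit of what is expected.** Also true. With independent misses the shortfall is 3–4 points at 15% and about nil at 10%. The larger losses need clustered misses, on which the plan gives no figure. The 6-of-7-day induction requirement, paid assessments and remote collection make wholly absent participants less likely. Still, 15% is the value the plan designed for and the reason for 125.
- **Covariate adjustment would add precision.** A gain of roughly 7–10% would restore 80% if misses are independent, but not if they cluster. The plan's own 80% claims no such gain.
- **68% and 83% may already count misses as positive.** Then 125 gives about 86%, but the inflation would serve no purpose. At 15% missing, collected samples would have to be 0.68/0.85 = 80% and 0.83/0.85 = 97.6% opiate-negative, and 0.85/0.85 = 100% buprenorphine-positive. At an assumed 92% collection the figures are less extreme: 74%, 90% and 92%. The division by 0.85 favours rates among collected samples, and the plan should say which it means.
- **The Primary Aim is against Usual Care, and the analysis without imputation is reported too.** Both stand and limit the consequence. Neither makes the 80% apply to the primary analysis of the contrast that sized the trial.

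**Conclusion.** The concern holds. The sample-size text and the primary missing-data rule describe two different analyses, and the 80% belongs to the one without imputation. The mismatch is plain from the text. Its direction holds wherever 106 per group means 80% power, both groups miss 15%, and 68% and 83% are rates among collected samples. The size is less certain: at two-sided 5%, the loss runs from 3–4 points with independent misses to about 19 points if the same people miss every visit. It shrinks, and can vanish, if collection is better than planned. Differences in collection between groups can move power either way. The shortfall is shown only for the contrast between the two Contingency Management groups. This should be fixed, but it does not undermine the adherence comparison with Usual Care.

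**What to change.** In Power Analyses and Total sample size:

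1. State the alpha and within-person correlation that give 106, and whether 68% and 83% are rates among collected or among all scheduled samples.
2. Add the power of that contrast under the primary rule. For example: *With 15% missing in each group, two-sided alpha 0.05 and within-person correlation [value used], scoring missing results as adverse gives 57.8% vs 70.6%; power at 125 per group is [lower] if whole participants are missing to [upper] if misses are independent, and is sensitive to unequal collection.* At correlation 0.70 the two entries are about 61% and 77%; the sponsor should insert the values that match its own correlation.
3. If the sponsor confirms the derivation, say that 106, 125 and 80% refer to the analysis without imputation: about 80% if whole participants are missing, up to about 84% if misses are scattered.
4. Note that 85% vs 45% adherence against Usual Care keeps power above 99%.

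This costs wording only, with no added participants or visits, provided the lower power is accepted and reported. Restoring 80% under the primary rule at 15% missing would take about 134–137 per group (independent misses) to 195–196 (whole participants missing). The drawback is a less favourable power figure for the contrast between the two Contingency Management groups.
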